## 7. Statistical considerations

### 7.1. Sample size consideration

This prospective non-interventional study is designed to evaluate and compare the performance of 6 imaging-guided techniques with wire-guided localization (WGL). It is hypothesized that the imaging-guided methods perform better or equal to WGL in terms of the likelihood of the intended lesion removal, as well as the likelihood of a negative margin. Each localization device/method will be compared to the wire-guided localization considered standard using propensity scoring. The first co-primary endpoint is the intended lesion removal. The failure rate of WGL in the literature is 0.6%, giving an identification rate of 99.4% [11]. A difference of 1.1% between techniques is considered to be clinically significant. Given an allocation rate of 2:1 for WGL : experimental group, sample sizes of 1854 in the WGL group and 927 in each experimental group are sufficient to restrict the upper boundary of the respective confidence interval for the differences in identification rates of WGL versus experimental device to 1.1% with a power of 80%. The other co-primary endpoint is the positive margin rate. The positive margin rate of WGL in the literature is 15%, yielding a negative margin rate of 85%, respectively [21]. A clinically significant difference between techniques was considered to be less than 5%. Assuming that each experimental method also has a negative margin rate of 85%, the upper limit of the confidence interval for the difference in negative margin rates is limited to 5% with a power of 80.04%. Each commercially available device will be analyzed in a separate cohort. To adjust for multiplicity and to keep an overall type 1 error of 5%, each of the 12 comparisons are planned with an alpha of 0.417%.

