### 7.2. Planned statistical analyses

This prospective cohort study has two independent primary endpoints A and B which will be tested 6 times each to compare each of the imaging-guided techniques separately with wire-guided localization as the gold standard. To control the family-wise error rate at 5% for the 12 tests, a Holm-Bonferroni procedure will be applied.

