### **Endpoint B**

Rate of negative resection margin rates (defined as lesion removal with no invasive or non-invasive carcinoma on ink) at first surgery, to be compared between imaging-guided techniques and WGL.

Hypotheses:

H20:  $P2_{\text{exp}_i} - P2_{\text{WGL}} \leq -0.05$  versus

H21:  $P2_{\text{exp}_i} - P2_{\text{WGL}} > -0.05$ ,

with  $P2_{\text{exp}_i}$ ,  $P2_{\text{WGL}}$  being the negative resection margin rates in the  $i$ th experimental group and in WGL group.

To balance the baseline variables between treatment groups, inverse-probability-of-treatment-weighting (IPTW) is applied to each pairwise comparison. Variables used for balancing include those variables that are associated with the outcome. The IPT weights will be considered for all primary endpoint comparisons.

Analysis of the primary endpoints:

The difference of the rates between the groups (WGL – experimental group  $i$ ) will be calculated and compared to the respective margin. The null hypothesis is rejected, if the lower bound of a defined confidence interval increases the margin.

To define the width of each confidence interval, the Holm-Bonferroni method will be applied:

1. Step: t-tests between each experimental method and WGL will be applied.
2. Step: The hypotheses are ordered by their nominal p-values. Only hypotheses indicating that the effectiveness of imaging-guided technique exceeds WGL are considered here. If none of the hypotheses shows this trend, the hypotheses are ordered by the lower bound of the 95% confidence interval of the estimated beta, starting with the highest number.
3. Step: For the first hypothesis in this order, a  $(100\% - \frac{5\%}{12})$ -confidence interval will be calculated. If the lower bound of this confidence interval increases the respective margin, the null hypothesis is rejected, and the next step will be applied. If the lower bound of this confidence interval does not increase the respective margin, the null hypothesis is accepted, and the procedure ends here.

4. Step: For the next hypothesis in this order, a  $(100\% - \frac{5\%}{11})$ -confidence interval will be calculated, and decisions are made as in the previous step. In each following step, the confidence interval gets incrementally larger, by dividing 5% through the number of untested hypotheses.

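### Step 2 of the Holm procedure drops any technique estimated at or below WGL before its non-inferiority test, so power per comparison at equal true rates is about 48–50%, not the stated 80%

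*Protocol*

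**What the plan says.** Protocol section 7.2 sets H11 and H21 as non-inferiority alternatives: experimental minus WGL greater than −0.011 for endpoint A and greater than −0.05 for endpoint B. There are six comparisons per endpoint, and the multiplicity rule is: "To control the family-wise error rate at 5% for the 12 tests, a Holm-Bonferroni procedure will be applied".

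The steps listed under Endpoint B then fix the algorithm. Step 1 runs t-tests of each method against WGL and mentions no margin. Step 2 orders the hypotheses by those p-values and adds: "Only hypotheses indicating that the effectiveness of imaging-guided technique exceeds WGL are considered here". Only if no hypothesis shows that trend does a fallback apply, in which "the hypotheses are ordered by the lower bound of the 95% confidence interval of the estimated beta, starting with the highest number". Steps 3 and 4 walk down this order with intervals at 5%/12, 5%/11 and so on, and stop at the first failure. No later step takes up the hypotheses that Step 2 left out.

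Section 7.1 gives the power: "sample sizes of 1854 in the WGL group and 927 in each experimental group are sufficient" for 80% (A) and 80.04% (B). For B it is explicit about the truth assumed: "Assuming that each experimental method also has a negative margin rate of 85" per cent.

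**The concern.** A non-inferiority claim does not need a favourable point estimate; it needs the confidence bound to clear the margin. A technique that is truly as good as WGL has roughly an even chance of an estimate at or below WGL. Under Step 2 that technique gets no test as long as any of the other 11 comparisons is positive, however tight its interval.

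This rule decides all 12 primary conclusions of a 7,416-patient cohort. If it is applied as written, about half of the truly equivalent comparisons end without a conclusion, and the power in section 7.1 does not describe the analysis in section 7.2. If the problem is noticed only once results are known, repairing it means a post-hoc change to the primary analysis.

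**Working it through.** **Inputs (section 7.1).** n = 1854 (WGL) and 927 (each technique). WGL rates are 99.4% (A) and 85% (B); margins are 0.011 and 0.05; alpha is 5%/12 = 0.417%. Equal true rates are stated for B. For A no experimental rate is given, so equality is an assumption here. Differences are experimental minus WGL, as in the hypotheses.

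**1. Reproducing the stated power.** SE = √[p(1−p)(1/1854 + 1/927)]; power = Φ(margin/SE − z).

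- B: SE = √(0.1275 × 0.0016181) = 0.01436, so margin/SE = 3.481. With one-sided z = 2.638, power = Φ(0.843) = 80.0%. The stated 80.04% is reproduced with alpha entered as 0.00417.
- A: SE = √(0.005964 × 0.0016181) = 0.003107, so margin/SE = 3.541 and power = Φ(0.903) = 81.7%. B drives the sample size (1853 WGL patients needed, against 1791 for A).
- With two-sided intervals (z = 2.865) the same formula gives 75.0% (A) and 73.1% (B), so section 7.1 evidently used a one-sided level.

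**2. What the filter discards.** At the strictest level, 5%/12 one-sided, the bound clears the margin when the estimate exceeds −margin + 2.638 × SE, using the planning SE:

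- A: −0.011 + 0.0082 = −0.0028
- B: −0.05 + 0.0379 = −0.0121

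So a technique estimated up to about 0.28 points (A) or 1.2 points (B) below WGL would meet its margin even at the first Holm step. Step 2 leaves it out.

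**3. Power as written, equal true rates.** The chance that the estimate exceeds WGL is 47.7% for A (exact binomial; ties take another 7.0%) and 49.5% for B. Given a positive estimate, the margin is cleared in more than 99.9% of cases, so power is essentially the chance of passing the filter. Single-step Bonferroni over all comparisons would reject in 77.3% (A) and 79.3% (B). About 30% of comparisons (77.3 − 47.7 = 29.6; 79.3 − 49.5 = 29.8) therefore meet the strictest level but fall to the filter.

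**4. Simulation of the whole procedure.** 200,000 trials, six techniques sharing one WGL group, binomial outcomes, no IPTW, fallback included, one-sided levels. Power per comparison, A / B:

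| True difference, A / B (points) | As written | Holm on 12 non-inferiority p-values |
|---|---|---|
| 0 / 0 | 48.3% / 49.5% | 90.2% / 91.8% |
| +0.1 / +1 | 61.0% / 75.5% | 97.0% / 99.0% |
| +0.2 / +2 | 74.4% / 92.2% | 99.3% / 99.9% |
| −0.2 / −1 | 29.6% / 24.2% | 62.3% / 66.0% |

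At equal rates the fallback is triggered in 1.0% of trials. The chance that a given technique passes on both endpoints is 24% as written and 84% under Holm. With two-sided intervals at equal rates, power as written is 48.3% / 49.3%, against 83.4% / 85.2% under Holm.

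**5. Filter or ordering?** Keeping the superiority order but testing all 12 hypotheses gives 89.1% / 89.7% at equal rates (one-sided). The ordering alone costs 1 to 2 points; the filter costs the rest.

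**The case against.** The best defence is textual. The sentence with the filter sits inside an ordering step, so it could mean only that favourable hypotheses are ranked first and the others follow. Step 4's division by the number of untested hypotheses, starting from 12 and then 11, fits a sequence through all 12. On that reading the 48–50% disappears. But no step places the remaining hypotheses in the order, and the fallback clause would be unnecessary if they always followed. The literal reading is the better supported one; at the least, the rule is not clear enough for a confirmatory analysis. If a favourable indication were taken to mean significantly better, power would be lower still.

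Three stronger readings are tempting but not supported:

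- *An absolute ceiling of 50%.* The figure belongs to equal true rates. Section 7.1 hypothesises better or equal performance, and power as written rises to 74% / 92% if techniques are truly better by 0.2 / 2 points.
- *Ordering by superiority tests invalidates Holm.* It does not. When the first true null hypothesis in any order is reached, the number still untested is at least the number of true nulls, so the level used is at most 5% divided by that number. Family-wise error stays controlled, and the filter can only remove rejections. The ordering is a small inefficiency at equal rates. It grows to 2.3 (A) and 5.3 (B) points if techniques are worse by 0.2 / 1 point.
- *The fallback order puts A before B, so that the stop rule blocks B.* This needs the estimated beta to be a raw risk difference, which the Protocol does not say. On a log odds ratio scale the order would tend to reverse. The fallback is also rarely reached at equal rates.

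It is also fair to say that the 90% / 92% comparator assumes one-sided levels and no weighting. Section 7.2 does not say whether its intervals are one- or two-sided, and IPTW will usually add variance. The comparator is therefore a range, not a promise.

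**Conclusion.** The point stands as a defect in the written rule. At equal true rates, Step 2 gives about 48% (A) and 50% (B) power per comparison, against 80% and 80.04% in section 7.1. Testing all 12 hypotheses by Holm on non-inferiority p-values would give 83–90% (A) and 85–92% (B), depending on whether the intervals are two- or one-sided. The shortfall as written hardly depends on that choice, because it is set by the sign of the estimate.

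The result rests on the literal reading of Step 2, equality of rates for A as an assumption, the planned group sizes, and unweighted analysis. The harm is missing conclusions about techniques that are as good as WGL, not false claims of non-inferiority. It should be corrected before outcomes are compared between techniques.

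**What to change.** Replace Steps 1 and 2 of section 7.2 with a rule along these lines: *For each of the 12 hypotheses, compute the one-sided non-inferiority p-value against its own margin (0.011 for A, 0.05 for B) from the IPT-weighted analysis. Order all 12 from smallest to largest and apply the Holm procedure.* Delete the restriction to techniques that look better than WGL, the fallback clause and the t-tests without a margin. Express Steps 3 and 4 as the matching one-sided bounds at 5%/12, 5%/11 and so on, so that they agree with the level that reproduces the 80.04%; if two-sided intervals are intended instead, restate the power.

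The change is to wording only. It needs no further patients or data, leaves family-wise error control intact, and raises power per comparison at equal rates from about 48–50% to 90–92% in the unweighted one-sided calculation. Removing the filter brings nearly all of that gain; the new ordering adds 1 to 2 points and ties the order to the hypotheses actually tested.

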## **8. Safety**

MELODY is a non-interventional study. All diagnostic and therapeutic procedures will be conducted according to national and institutional standards in the clinical routine. One of the secondary endpoints of the study is the evaluation of safety of different types of lesion localization, particularly with regard to lost marker rates and localization failure.

## **9. Funding**

Study support is currently applied for.

## 11. Protocol Change Log

Version	Changes
1.3	Section “Statistical considerations” extended [no versions between 1.0.18 and 1.3; version number changed to 1.3 to align with version numbers of the German protocol]
1.0.18	List of National Steering Committees updated (Egypt) Title of [name] updated Title of [name] updated
1.0.17	List of National Steering Committees updated (Korea)
1.0.16	Signature Page added
1.0.15	Responsibility for data management specified
1.0.14	List of National Steering Committees updated (Pakistan)
1.0.13	List of National Steering Committees updated (Argentina)
1.0.12	List of National Steering Committees updated (Peru)
1.0.11	List of National Steering Committees updated (Greece)
1.0.10	List of National Steering Committees updated (Portugal)
1.0.9	List of National Steering Committees updated (Ireland)
1.0.8	List of National Steering Committees updated (Denmark)
1.0.7	List of National Steering Committees updated (Austria) and responsibility for data management updated (EUBREAST)
1.0.6	List of National Steering Committees updated (Spain)
1.0.5	List of National Steering Committees updated (Sweden, India)
1.0.4	List of National Steering Committees updated (France added)
1.0.3	Affiliation of the Head of National Steering Committee in Italy updated
1.0.2	List of National Steering Committees updated
1.0.1	Protocol Change Log added Representative of the OPBC [name] added as member of the ISB List of National Steering Committees updated Affiliation of [name] updated
